5.6 PARTICIPANT WITHDRAWAL OR TERMINATION

5.6.1 REASONS FOR WITHDRAWAL OR TERMINATION

Best efforts will be made to encourage subjects to attend all study visits. Subjects will be informed that they are free to withdraw from the study at any time and for any reason. A discontinuation from the study will occur when a subject who signed informed consent and was dosed ceases participation in this study, regardless of circumstances.

Subjects can be discontinued from the study for one of the following reasons:

- AE
- Total or partial knee replacement of the target knee
- Lost to follow-up after a minimum of 3 attempts have been made to contact the subject, including sending a registered letter
- Withdrawal by subject for reason other than lack of efficacy
- Subject noncompliance
- Physician decision for reason other than lack of efficacy
- Study terminated by Sponsor
- Site terminated by Sponsor

- Request by regulatory authority
- Lack of efficacy
- Pregnancy
- Death
- Other

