3.2.4 Other Endpoints

1. Change from parent-study and OA-07-study baseline in medial joint space width (mJSW) as documented by radiograph of the target knee at Visit 2E (Week 24)
2. Change from parent-study and OA-07-study baseline OA pain, function, and stiffness as a composite outcome measure as assessed by WOMAC Total score and Stiffness at Visit 2E (Week 24) and Visit 3E (Week 48)
3. Change from parent-study and OA-07-study baseline in mJSW, pain NRS, WOMAC Pain, and WOMAC Function at Visit 6E (Week 100) compared to test values (carry forward and progression assumptions) derived from the change from baseline estimates from the Placebo group at Visit 3E (Week 48)
4. Change from parent-study baseline health-related quality of life (HRQOL) as assessed by the 36-Item Short Form Health Survey (SF-36) at Visit 3E (Week 48)
5. Percentage of subjects who consider themselves to be in Patient Acceptable Symptom State (PASS) at Visit 3E (Week 48)

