7. GENERAL ISSUES FOR STATISTICAL ANALYSIS

7.1 General Statistical Methodology

Unless otherwise specified, efficacy analyses will be performed on the FAS, PPAS, and mFAS; general safety, bone imaging, and biomarker analyses will be performed on the SAS. The number of evaluable subjects in any analysis set may vary by endpoint/timepoint based on missing data.

For continuous variables, the outcome measure at each visit, as well as the absolute change (outcome at visit – outcome at baseline), will be summarized within each treatment group using descriptive statistics (number of subjects, mean, SD, median, minimum, and maximum). Categorical variables will be summarized with counts and percentages.

Data collected from unscheduled visits will not be included in summary tables but will be included in subject-level listings as appropriate.

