7.1.4 Imputation of Missing Data

Sensitivity analysis will be performed using multiple imputation (MI) for the primary and secondary endpoints. Missing data will be imputed based upon the observed data for each outcome under the MAR assumption following the paradigm first developed by Rubin (Shafer, 1999). The imputation will adjust for the outcome's baseline data in a regression model with data imputed independently for each timepoint. A total of 10 imputation datasets will be created and analyzed based upon accepted convention (Shafer, 1999). Error estimates of the multiple imputation itself, as well as an overall summary of the efficacy analysis, will be averaged across the 10 imputed datasets based upon Rubin's paradigm.

Specifically, let Q denote the imputed mean of an efficacy outcome Y subject to missing data at a given timepoint, where the estimate of that mean for any i^{th} imputation would be defined as function of both observed and missing such that

$$\widehat{Q^{(i)}} = E\left(Q^{(i)} | Y_{observed}, Y_{missing}^{(i)}, Y_{Baseline}, I(Group)\right), i = 1, \dots, 10.$$

After all 10 datasets have been imputed, the overall estimate of Q is a simple average defined as

$$\bar{Q} = \frac{\sum_{i=1}^{10} \widehat{Q}^{(i)}}{10}.$$

For this analysis using 10 imputed datasets, the variance of \bar{Q} is defined as

$$Var(\bar{Q}) = 1.1B + \bar{U}$$

where B is the between imputation variance and U is the within imputation variance:

$$B = \frac{1}{9} \sum_{i=1}^{10} \left(\widehat{Q}^{(i)} - \bar{Q} \right)^2;$$

$$\bar{U} = \frac{\sum_{i=1}^{10} U^{(i)}}{10}.$$

PROC MI in SAS® will be used to impute missing data assuming missingness is monotone in pattern. If a subject is missing a baseline record causing non-monotone missingness, all non-missing post-baseline records will temporarily be set to missing as well. After the 10 imputation datasets are created, the non-missing post-baseline will be merged back in, thus creating complete datasets where only the originally missing records were imputed. Imputations will be performed with a seed of 469007.

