9.6 Other Efficacy Analysis

The analyses described below will be performed on subjects in the FAS, mFAS, CAS, and PPAS.

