9.6.3 PASS and Response Analysis

The number and percent of subjects reporting “Yes” to Patient Acceptable Symptom State (PASS) at Visit 3E (Week 48) and Visit 6E (Week 100) will be summarized. Logistic regression analysis will be implemented for “Yes” responses in PASS adjusted for their response at Visit 1E (Day 1), with 95% confidence intervals and P values reported.

The number and percent of subjects reporting Outcome Measures in Rheumatology Clinical Trials (OMERACT)-Osteoarthritis Research Society International (OARSI) ‘strict’ responders will be summarized. An OMERACT-OARSI ‘strict’ responder must have a 50% improvement with corresponding 20 point (out of 100) actual scale improvement in pain or function outcomes. Two ‘strict’ responder outcomes will be estimated, one using WOMAC Pain and WOMAC Function and the other using Pain NRS (2-point improvement out of 10) and WOMAC Function.

Additionally, the number and percent of subjects reporting 20% improvement, 30% improvement, 50% improvement, and 70% improvement in Pain NRS, WOMAC Pain, and WOMAC Function will be summarized. Logistic regression analysis will be implemented for improvement in these assessments as well, with 95% confidence intervals and P values reported.

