	Sensitivity 2	Change from parent-study baseline in mJSW at Visit 2E (Week 24)	mFAS	Prohibited medications and NSAID/acetaminophen use: treatment policy strategy; analysis will be conducted regardless of use of prohibited medications or NSAID/acetaminophen use.	Difference in the change from baseline between LOR and placebo using parent-study baseline-adjusted ANCOVA with available data.
	Sensitivity 3	Change from parent-study baseline in mJSW at Visit 2E (Week 24)	PPAS	1) Prohibited medications: principal stratum strategy; subjects who used prohibited medications will be excluded from this analysis. 2) NSAID/acetaminophen: treatment policy strategy; analysis will be conducted regardless of NSAID/acetaminophen use.	Difference in the change from parent-study baseline between LOR and placebo using parent-study baseline-adjusted ANCOVA.
Estimand is repeated using the OA-07-study baseline					

Other	Estimator	Variable	Population	Other intercurrent events	Population level summary
	Main	Change from parent-study baseline in WOMAC Total at Visit 3E (Week 48)	FAS	Prohibited medications and NSAID/acetaminophen use: treatment policy strategy; analysis will be conducted regardless of use of prohibited medications or NSAID/acetaminophen use.	Difference in the change from parent-study baseline between LOR and placebo using parent-study baseline-adjusted ANCOVA with available data.
	Sensitivity 1	Change from parent-study baseline in WOMAC Total at Visit 3E (Week 48)	FAS	Prohibited medications and NSAID/acetaminophen use: treatment policy strategy; analysis will be conducted regardless of use of prohibited medications or NSAID/acetaminophen use.	Difference in the change from parent-study baseline between LOR and placebo using parent-study baseline-adjusted ANCOVA with missing data imputed using the MI method.
	Sensitivity 2	Change from parent-study baseline in WOMAC Total at Visit 3E (Week 48)	mFAS	Prohibited medications and NSAID/acetaminophen use: treatment policy strategy; analysis will be conducted regardless of use of prohibited medications or NSAID/acetaminophen use.	Difference in the change from parent-study baseline between LOR and placebo using parent-study baseline-adjusted ANCOVA with available data.

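### SAP 9.6.3 sets no denominator or missing-response rule for PASS and responder outcomes, so knee-replacement subjects and some lack-of-efficacy leavers appear to be left out rather than counted as failures

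*SAP*

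**What the plan says.** **Outcomes.** SAP 9.6.3 plans counts and percentages for PASS, for two versions of 'strict' response, and for "the number and percent of subjects reporting 20% improvement, 30% improvement, 50% improvement, and 70% improvement in Pain NRS, WOMAC Pain, and WOMAC Function". PASS is modelled by logistic regression adjusted for the Visit 1E answer. For the percent-improvement outcomes, "Logistic regression analysis will be implemented for improvement in these assessments as well, with 95% confidence intervals and P values reported". 'Strict' response is summarised but not modelled. The section is silent on the denominator and on a missing response. The only general rule is in SAP 7.1: "The number of evaluable subjects in any analysis set may vary by endpoint/timepoint based on missing data".

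**Imputation.** SAP 7.1.4 states: "Sensitivity analysis will be performed using multiple imputation (MI) for the primary and secondary endpoints". PASS is an Other endpoint (SAP 3.2.4), and the responder outcomes are not in the SAP 3.2 list at all. Appendix 2 goes further than 7.1.4. It gives MI rows to some Other endpoints (mJSW at Visit 2E, WOMAC Total, WOMAC Stiffness), for example "Difference in the change from parent-study baseline between LOR and placebo using parent-study baseline-adjusted ANCOVA with missing data imputed using the MI method". It has no row for PASS or for any responder outcome.

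**Repeats.** SAP 9.6 says of everything in that section: "The analyses described below will be performed on subjects in the FAS, mFAS, CAS, and PPAS".

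**Exits.** Protocol 5.6.1 lists lack of efficacy and "Total or partial knee replacement of the target knee" among the reasons for discontinuation. Protocol 5.6.2 asks for all Termination Visit assessments in withdrawers, and Protocol 7.3.3 includes pain NRS, WOMAC and PASS among them. The same section waives all three after knee replacement. SAP 7.1.3 attaches early-termination scores to a scheduled visit only if they were taken during it.

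**The concern.** A response percentage is naturally read as the share of treated subjects who did well. If subjects without a score drop out of both numerator and denominator, it becomes the share among those who stayed and were scored. For subjects who have had the target knee replaced, the missing score follows from the protocol itself, after a recorded outcome event.

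Leaving such subjects out raises the response percentage in both arms, by more in the arm with more such exits. A treatment that prevented them would get no credit, and one that led to them would not be penalised. The odds ratios and P values for PASS and percent improvement would carry the same restriction without saying so.

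**Working it through.** The plan gives no response rate, exit rate or power figure for these outcomes, so there is no figure to reproduce. The check is a reading of the text followed by an illustration.

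**1. Which leavers have a score at Visit 3E?**
- *Target-knee replacement:* the subject is discontinued and NRS, WOMAC and PASS are not required. No score is expected.
- *Lack of efficacy:* termination scores are expected, but SAP 7.1.3 keeps them only if taken during a scheduled visit. Assume termination visits are spread evenly over weeks 0 to 52, and that the phrase means the ±4-week window around Week 48. About 8/52 = 15% would then map to Visit 3E. Both assumptions are mine.
- No rule carries other termination scores to Visit 3E or Visit 6E.

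**2. Does a planned analysis bring them back?**
- *MI:* not planned for the binary outcomes in SAP 7.1.4, SAP 9.6 or Appendix 2. It is planned for continuous pain NRS, WOMAC Pain and WOMAC Function at Visits 2E and 3E, but response is not derived from the imputed values. That MI assumes MAR and adjusts for the outcome's baseline, so it does not use the reason for leaving.
- *Other analysis sets:* mFAS requires completion of Visit 3E, CAS an mJSW result at Visit 6E, and PPAS completion of Visit 6E. Each conditions further on staying.
- *Estimands:* Appendix 2 addresses use of prohibited medication and of NSAIDs or acetaminophen, but not discontinuation or knee replacement.

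**3. Illustration.** Let r be the response rate among scored subjects and f the share leaving as failures without a score.
- Rate with leavers counted as failures: r × (1 − f).
- Shift in the LOR-minus-placebo difference: r_P × f_P − r_L × f_L.

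The SAP's total of about 500 (SAP 5) is taken as 250 per arm. Equal arms and all values of r and f are assumptions.

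| Scored response, LOR v placebo | Failure exits, LOR / placebo | Leavers counted as failures | Difference in points, before → after |
|---|---|---|---|
| 50% v 50% | 5% / 10% | 47.5% v 45.0% | 0 → +2.5 |
| 50% v 50% | 10% / 5% | 45.0% v 47.5% | 0 → −2.5 |
| 50% v 45% | 10% / 5% | 45.0% v 42.75% | 5.0 → 2.25 |
| 60% v 50% | 5% / 10% | 57.0% v 45.0% | 10.0 → 12.0 |
| 60% v 50% | 10% / 5% | 54.0% v 47.5% | 10.0 → 6.5 |
| 60% v 50% | 10% / 10% | 54.0% v 45.0% | 10.0 → 9.0 |
| 60% v 50% | 5% / 15% | 57.0% v 42.5% | 10.0 → 14.5 |
| 60% v 50% | 15% / 5% | 51.0% v 47.5% | 10.0 → 3.5 |

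Standard error of the difference near 50% response: √(2 × 0.25/250) = 0.0447, about 4.5 points.

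By a two-sided pooled z test, the 10% / 10% row moves from p = 0.033 to 0.044, and the 15% / 5% row from p = 0.033 to 0.43.

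**The case against.** The strongest reply is that this is a gap in wording, in low-tier analyses, from which it is easy to infer too much. Several parts of that reply stand.

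- A reader might infer that the SAP restricts these analyses to scored subjects. It does not say so. Observed-case analysis is the natural reading of SAP 7.1 and of a logistic regression with no imputation rule, but a percentage of subjects could also be taken over the whole FAS.
- A reader might infer that every lack-of-efficacy leaver is lost. Termination scores are requested, and those taken at a scheduled visit are kept under SAP 7.1.3.
- A reader might say that the leavers' status is known to be non-response. It is not. Response is defined by a score or by the subject's own PASS answer, and someone who leaves for lack of efficacy may still be 20% better than baseline. Scoring such exits as failures is a composite-strategy choice: conventional, but one that has to be stated.
- A reader might say that nothing in the plan would reveal the problem. SAP 8.1 tabulates discontinuation reasons by arm, so an imbalance would be visible, though nothing links it to response.
- After Visit 3E all subjects receive LOR, so the two-arm argument does not extend to PASS at Visit 6E.
- With a 5-point imbalance in exits, the shift is smaller than the standard error.

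What the reply does not remove is the gap itself. No denominator, missing-response rule or sensitivity analysis is stated for binary outcomes that are reported with P values, and the subjects most clearly affected have their scores waived by the protocol.

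**Conclusion.** The concern holds as a specification gap. Followed as written, the plan most likely yields observed-case response rates and odds ratios. These leave out target-knee replacements and those lack-of-efficacy leavers without a score at the visit, and the planned repeats would not show the effect.

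Its size cannot be taken from the documents. A 5-point imbalance in failure exits moves the difference by 2.5 to 2.75 points when response is 45% to 50%, and by 2.0 to 3.5 points at 60% v 50%. A 10-point imbalance at 60% v 50% moves it by 4.5 to 6.5 points. Equal exits only shrink it modestly. All of this rests on the assumed exit rates, response rates and equal arms.

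A reader might conclude that the comparison is biased towards LOR. The documents do not support that: with no exits by arm and reason, the shift could go either way. Primary and secondary results do not depend on it. The change is worth making but not critical.

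**What to change.** In SAP 9.6.3, for the LOR versus placebo comparisons through Visit 3E:

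1. State the FAS as the denominator.
2. Score as non-responder (PASS 'No') any subject with target-knee replacement before the visit, and any subject who discontinued for lack of efficacy and has no score mapped to that visit under SAP 7.1.3. A mapped score from a lack-of-efficacy leaver is kept.
3. For other missingness at Visits 2E and 3E, derive percent-improvement and 'strict' response from the planned imputed NRS and WOMAC values. PASS is not imputed anywhere, so either score a missing answer as 'No' or report observed cases with the number missing by arm. Choose one and state it.
4. Report the observed-case version alongside as a sensitivity analysis.
5. Label the Visit 6E summaries as uncontrolled.

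If another strategy is preferred, the denominator and missing-response rule still have to be written down.

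Cost: a few sentences in the SAP, a little extra programming using the discontinuation reason already on the eCRF (Protocol 5.6.2), and slightly lower response percentages in both arms. The sponsor was unblinded once the parent-study database was locked (SAP 4.4), so the change should be dated and entered in SAP 13. Showing both versions lets a reader see that the rule was not chosen for its result.

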9.6.4 Concordance Analysis

Logistic regression will be conducted within each treatment group to determine whether parent-study baseline-adjusted change in mJSW is concordant with response criteria for Pain NRS, WOMAC Pain, and WOMAC Function. Response criteria will model 20%, 30%, 50%, and 70% improvement in each outcome. Each outcome will be modeled individually. Receiver operator characteristic (ROC) areas under the curve (AUC) will be provided, along with odds ratios and 95% confidence intervals. The analysis will be repeated using OA-07-study baseline-adjusted change as well as OA-07 Visit 3E (Week 48) baseline-adjusted change as follows:

Group of interest	Baseline	Visit
LOR-LOR ¹	Parent-Study	Visit 3E (Week 48)
		Visit 6E (Week 100)
	OA-07-Study	Visit 3E (Week 48)
		Visit 6E (Week 100)
Placebo-Placebo ²	Parent-Study	Visit 3E (Week 48)
		Visit 6E (Week 100)
	OA-07-Study	Visit 3E (Week 48)
		Visit 6E (Week 100)
Placebo-LOR ³	OA-07-Study Visit 3E (Week 48)	Visit 3E (Week 48)
		Visit 6E (Week 100)

¹ Includes subjects treated with, at least, LOR during the OA-11 study and LOR at the OA-07 Visit 1E (Day 1)

² Includes subjects treated with, at least, PBO during the OA-11 study and PBO at the OA-07 Visit 1E (Day 1)

³ Includes subjects treated with, at least, PBO during the OA-11 study, PBO at the OA-07 Visit 1E (Day 1) and LOR at the OA-07 Visit 3E (Week 48)

9.6.5 Open Label Portion of Study (Placebo Subjects Cross Over to LOR)

On and after Visit 3E (Week 48) all subjects only received LOR injections.

9.6.5.1 Groups of interest

The following groups will be analyzed:

- “Placebo-LOR” group includes subjects treated with Placebo during the OA-11 study, Placebo at the OA-07 Visit 1E (Day 1) and LOR at the OA-07 Visit 3E (Week 48).
- “LOR-LOR” group includes subjects treated with LOR during the OA-11 study, LOR at the OA-07 Visit 1E (Day 1) and LOR at the OA-07 Visit 3E (Week 48).
- Pooled “Placebo-LOR” and “LOR-LOR” groups.

9.6.5.2 Analysis

For each group of interest described in Section 9.6.5.1, we will estimate an mJSW baseline-adjusted ANCOVA at Visit 6E (Week 100) and test the difference against two test values:

- Carry-forward (i.e., no change) assumption test value will use the mJSW baseline-adjusted ANCOVA estimate at Visit 3E (Week 48) from the Placebo group.
- Progression (i.e., worsening) assumption test value will use the mJSW baseline-adjusted ANCOVA estimate at Visit 3E (Week 48) from the Placebo group extrapolated to a presumption of continued Placebo use.

Analysis will be performed using the parent and OA-07 study baselines.

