10.4.3 ANALYSIS OF EFFICACY ENDPOINT(S)

Change over time through Visit 3E in mJSW, pain NRS, WOMAC Pain, WOMAC Function, and WOMAC Total will be characterized using mixed-effects models for repeated measures (MMRM). The models will estimate change from parent-study baseline with treatment, visit, treatment \times visit interaction, and parent-study baseline value as covariates. Unadjusted 95% confidence intervals and *P* values will be reported. The potential confounding effect of change in NSAID/acetaminophen usage on the treatment effect will be considered for sensitivity analysis.

ANCOVA will be used to analyze the change in SF-36 domain scores and summary component scores through Visit 3E. Change will be assessed from parent-study baseline between the active and placebo treatment groups. The models will be adjusted for parent-study baseline. Unadjusted 95% confidence intervals and *P* values will be reported.

PASS will be analyzed using logistic regression. Logistic regression will also be used to compare the proportion of Outcome Measures in Rheumatology Clinical Trials (OMERACT)-Osteoarthritis Research Society International (OARSI) responders and “strict” responders ([Pham et al. 2003](#)) between treatment groups through Visit 3E, as well as proportion of subjects achieving a 20%, 50%, and 70% improvement.

Maintenance of LOR’s effects on pain and function of the target knee will be characterized by summarizing likelihood of response in pain NRS, WOMAC Pain, and WOMAC Function in the current study for those subjects that had a response in the parent study. Response will be characterized as a 20%, 50%, and 70% improvement.

After all subjects have received LOR at Visit 3E, all further efficacy analyses will be descriptive in nature.

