4.3 Method of Treatment Assignment and Randomization

Subjects were randomized in the SM04690-OA-11 study. Each subject maintained the same treatment assignment of LOR or placebo as in the parent study at Visit 1E (Day 1). At Visit 3E

(Week 48) and for any subsequent injections until the Termination Visit, all subjects received LOR injection(s).

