6. The least squares estimate of improvement from parent-study baseline in medial joint space width in the target knee at Visit 6E (Week 100) is greater for subjects who received “Placebo-LOR”, “LOR-LOR” and All (pooled “Placebo-LOR” and “LOR-LOR”) subjects compared to test values (carry forward and progression assumptions) derived from the change from baseline estimates from the Placebo group at Visit 3E (Week 48)

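### The Week 100 mJSW tests set LOR-treated groups against values built from Week 48 placebo data; adding a Week 100 comparison of the two randomised arms would remove the bias from change common to both.

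*SAP*

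**What the plan says.** SAP 9.6.5.1 defines three groups: Placebo-LOR, LOR-LOR and the two pooled. For each one separately, SAP 9.6.5.2 says "we will estimate an mJSW baseline-adjusted ANCOVA at Visit 6E (Week 100) and test the difference against two test values".

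- The first: "Carry-forward (i.e., no change) assumption test value will use the mJSW baseline-adjusted ANCOVA estimate at Visit 3E (Week 48) from the Placebo group".
- The second is the same Week 48 estimate "from the Placebo group extrapolated to a presumption of continued Placebo use". No rate or formula is given.

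Other hypothesis 6 in SAP 9.1 says improvement will be greater "compared to test values (carry forward and progression assumptions) derived from the change from baseline estimates from the Placebo group at Visit 3E". SAP 9.2 (other hypothesis 6) and Appendix 2 repeat this for the OA-07-study baseline. Endpoint 3 of SAP 3.2.4 applies the same test values to pain NRS, WOMAC Pain and WOMAC Function.

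Between-arm mJSW ANCOVAs are planned at Visit 2E and Visit 3E only (SAP 9.4, 9.5, 9.6.1, 9.6.2). The arms themselves are still identifiable: "Subjects were randomized in the SM04690-OA-11 study" (SAP 4.3), and subjects kept that assignment at Visit 1E.

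Protocol 10.4.3 had said that once all subjects have received LOR at Visit 3E, "all further efficacy analyses will be descriptive in nature". SAP section 13 declares the departure from this.

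**The concern.** Between Week 48 and Week 100, mJSW can change for reasons that have nothing to do with LOR: narrowing may continue, slow or stop, and image reading may drift. A between-arm contrast at one visit cancels such change. A comparison of one group at Week 100 with a value fixed at Week 48 does not. The pooled test shows this most clearly, because both randomised arms sit on the same side and are compared with a number.

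At stake is how a significant Week 100 result would be read. Beating the progression value could mean that LOR preserved joint space, or only that narrowing slowed in everyone. The study has no placebo data after Week 48 to tell these apart.

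**Working it through.** **Nothing to reproduce.** The documents give no power, effect size, SD or expected progression for these tests, and the figure of about 500 subjects is practical (SAP section 5).

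**Bias.** Let e be the LOR effect in a group, c the Week 48 to 100 change common to both arms, m the placebo change at Week 48, and k the extrapolation factor. The group mean at Week 100 is m + c + e.

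- Carry-forward: (m + c + e) - m = e + c.
- Progression: (m + c + e) - km = e + c - (k-1)m.
- LOR-LOR minus Placebo-LOR at Week 100: e(LOR-LOR) - e(Placebo-LOR). Both c and m cancel.

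Carry-forward is unbiased only if c = 0, and progression only if c = (k-1)m. With k > 1 and m not zero, both cannot hold.

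**Extrapolation factor.** The SAP states none. If it is linear in time:

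- Parent baseline: Visit 3E falls at 56 + 48 = 104 weeks and Visit 6E at 56 + 100 = 156, so k = 156/104 = 1.50. With the full 6-week entry window, k = 162/110 = 1.47.
- OA-07 baseline (X-ray at parent Week 52): k = 104/52 = 2.00, or 110/58 = 1.90 with the window.

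**Size.** Assumed, because the documents give no values: SD of change 0.6 mm at Visit 3E and 0.69 mm at Visit 6E, correlation 0.7, n = 150 per arm, m = -0.2 mm, k = 1.5, two-sided 5% (2.5% in the favourable direction). The covariance is 0.7 x 0.6 x 0.69 = 0.2898. The standard error includes placebo sampling error and the shared subjects, so what remains is bias.

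Variance of the progression difference, times n:

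- Placebo-LOR: 0.4761 + 2.25 x 0.36 - 2 x 1.5 x 0.2898 = 0.4167; SE = 0.0527.
- LOR-LOR: 0.4761 + 0.81 = 1.2861; SE = 0.0926.
- Pooled: 0.4761/2 + 0.81 - 1.5 x 0.2898 = 0.6134; SE = 0.0639.

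With an inert drug and no further change (e = 0, c = 0), the expected difference is -0.2 + 0.3 = +0.1 mm. The probability of a false benefit claim is Phi(0.1/SE - 1.96):

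| Group | 0.1/SE | False benefit vs progression |
|---|---|---|
| Placebo-LOR | 1.90 | 47% |
| LOR-LOR | 1.08 | 19% |
| Pooled | 1.56 | 35% |

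If narrowing continues at half the assumed rate (c = -0.05, difference +0.05 mm), the same formula gives 16%, 8% and 12%.

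**Range.** From m = -0.1 mm with 100 per arm to m = -0.3 mm with 250 per arm, case c = 0 gives 12-96% (Placebo-LOR), 6-55% (LOR-LOR) and 9-86% (pooled). The top end needs about 500 subjects imaged at Week 100 with no attrition.

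**Carry-forward when narrowing continues.** With c = -0.1 mm, the LOR-LOR variance times n is 0.4761 + 0.36 = 0.8361, so SE = 0.0747 and z = -1.34. A false benefit claim then has probability Phi(-1.34 - 1.96), about 0.05%, which is far below 2.5%.

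**Arm contrast.** In simulations with no LOR effect, with c from -0.2 to +0.1 SD, a Week 100 ANCOVA of the two arms rejected in 4.0% to 5.8% of trials in all 14 scenarios (nominal 5%). Its 95% CI half-width under the assumptions above is 1.96 x 0.69 x sqrt(2/150) = 0.16 mm.

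**The case against.** The strongest reply is that the SAP brackets the unknown. It gives a no-change and a worsening value, calls both assumptions, places these analyses in its lowest tier, describes the period as open-label and uncontrolled, and declares the departure from the protocol. By-arm Week 100 values will also appear descriptively (SAP 7.1). All of this stands. But the bracket describes uncertainty about the comparator, whereas the plan attaches a hypothesis test to each end.

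Four stronger readings are tempting, and the documents do not support them.

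- A reader might infer that both tests credit LOR with all common change. The progression value is itself an adjustment for time, so only the departure from the assumed progression is credited.
- A reader might infer that the plan will falsely find LOR harmful if narrowing continues. Other hypothesis 6 is directional, towards benefit. The generic ANCOVA alternative in SAP 7.1.2 is two-sided, so an adverse result could be reported, but for a benefit claim carry-forward is then conservative.
- A reader might infer that these are the only inferential long-term results. SAP 9.6.3 summarises PASS at Visit 6E and plans a logistic regression without tying it to a visit. SAP 9.6.4 gives odds ratios and confidence intervals at Visit 6E.
- A reader might take 1.5 or 2 as the planned extrapolation factor. It is inferred here from the visit schedule.

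It is also fair to say that the arm contrast cannot answer LOR versus placebo at Week 100, and that adding it is a further departure from the protocol's descriptive-only rule.

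**Conclusion.** The point holds. At Week 100 the planned mJSW tests cannot separate a LOR effect from change common to both arms (carry-forward), or from common change that differs from an unstated projection (progression). The same applies to the pain and function comparisons under endpoint 3 of SAP 3.2.4. At least one test is biased whenever placebo change is not zero and the extrapolation departs from no change, and a correct standard error does not cure this.

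That conclusion is algebraic and needs no assumed figures. The rates of 47%, 19% and 35% rest wholly on the assumed SDs, correlation, arm size, placebo change and linear factor, and the range is wide. They illustrate the problem; they do not predict this trial's error rate. The Visit 3E primary and secondary analyses are between-arm contrasts and are unaffected. A cheap remedy exists in data already collected.

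**What to change.** In SAP 9.6.5.2, 9.1 (other hypothesis 6), 9.2 (other hypothesis 6) and Appendix 2, add a baseline-adjusted ANCOVA of change in mJSW at Visit 6E.

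- Compare arms as randomised in the parent study, not groups defined by having received the Visit 3E injection. Use FAS subjects with Week 100 data, and apply the multiple imputation of SAP 7.1.4 as a sensitivity analysis.
- Report the estimate and 95% CI, labelled as an exploratory comparison of early with delayed start of LOR among parent-study completers who continued.
- Declare it in section 13 as a further departure from Protocol 10.4.3. Correct that section's pointer to 9.4.4 at the same time: no such section exists, and the text is in 9.6.5.

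Present the carry-forward and progression comparisons, including those for pain and function under endpoint 3 of SAP 3.2.4, as descriptive reference displays. State the extrapolation formula, and draw no conclusion of benefit over placebo at Week 100 from them.

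The cost is SAP wording and one extra model. The sponsor gives up tests against assumed placebo values. The new contrast answers a narrower question than LOR versus placebo, may be small if delayed-start subjects catch up, and is open to selection through continued participation.
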